# IPSEN GROUP D-FR-52120-223 CONFIDENTIAL

### PROTOCOL: FINAL VERSION 3.0: 16 APRIL 2018

**PAGE 35/139** 

Subjects will be followed-up by telephone at Week 1 and Week 4; and will attend clinic visits at Week 2, Week 6 (primary study timepoint), and Week 12. Thereafter telephone visits will be scheduled every 12 weeks until end of study (EOS), or until retreatment is required. Details of the procedures performed at each study visit are described in Section 5.

The study design allows for subjects to request retreatment if clinically required after a minimum of 12 weeks following the previous IMP administration (see Section 5.2.5.3). The retreatment request may come at a scheduled visit or between visits. Subjects who request retreatment will be assessed and if they satisfy the retreatment criteria (Section 4.3) a Retreatment Visit will be scheduled for administration of the retreatment. All retreatments within the study are double blind treatments of either 600 U or 800 U of Dysport®. Follow-up after each retreatment will be per the same schedule as the first treatment (although antibody testing at Week 6 is performed only after the first IMP administration).

Subjects should exit the study 104 weeks (2 years) after the first IMP administration. However, all subjects will be followed-up for at least 12 weeks after each retreatment; therefore, a subject who receives a study retreatment between Week 92 and Week 104 will have their study exit delayed until the Follow-up Visit scheduled for 12 weeks after their most recent retreatment.

An overview of the study design is presented in Figure 1 and a visit flow chart is presented in Figure 2.

[figure not shown]
PAGE 36/139

PROTOCOL: FINAL VERSION 3.0: 16 APRIL 2018

Sequence 1 Sequence 3 Sequence 2 Sequence 4 Week 104 to 116 depending on timing of last study **EOS Visit** May occur a minimum of 12 weeks following previous treatment (on patient request and if retreatment criteria are met) Dysport 800 U Dysport 600 U Dysport 800 U Dysport 600 U Retreatments Figure 1 Study Design Week 12 Dysport 600 U Dysport 800 U Placebo Placebo Randomisation and first treatment Screening period

U=unit; EOS=End of Study.

treatment.

EOS=End of Study

**PAGE 38/139** 

#### 3.2 Primary and Secondary Endpoints and Evaluations

#### 3.2.1 Primary Efficacy Endpoint and Evaluations

Mean change from study Baseline (assessed at Screening) to Week 6 after the first IMP administration in the weekly number of UI episodes:

measured on a 7-day bladder diary.

Seven-day bladder diaries that contain data recorded on at least 5 days will be included in the analysis. Where there are 1 or 2 days with no data, the arithmetic means will be used from the bladder diary parameters recorded on the 5 or 6 days that do have events recorded; for the days with no recorded bladder diary data.

# 3.2.2 Secondary Efficacy Endpoints and Evaluations

# 3.2.2.1 Overview of Secondary Measures

Mean change from study Baseline (assessed at Screening) or from treatment cycle baseline (assessed at Retreatment Assessment Visit) to post-treatment timepoints (timepoints listed in Table 4 and Table 5):

- Bladder diary measures:
  - weekly number of UI episodes
  - daily urinary frequency (total, spontaneous void only, CIC only)
  - 24-hour voided volume (total, spontaneous void only, CIC only)
  - volume per void (total, spontaneous void only, CIC only).
  - Urodynamic filling cystometry measures (urodynamic subset only):
    - maximum cystometric capacity (MCC)
    - maximum detrusor pressure (MDP) during storage
    - volume at first involuntary detrusor contraction (Vol@1stIDC) (subjects without a post-treatment IDC will have their Vol@1stIDC imputed from their MCC)
    - maximum detrusor pressure at first involuntary detrusor contraction (PdetMax@1stIDC)
    - end fill pressure (EFP)
    - detrusor compliance (DC).
- Patient-reported outcome questionnaires:
  - incontinence quality of life (I-QoL) total summary score
  - EuroQol 5-dimension 5-level (EQ-5D-5L)
  - modified patient global impression improvement (mPGI-I) score (to be assessed at each timepoint without comparison to baseline).

Proportion of subjects at post-treatment timepoints following the first and subsequent treatments with:

- no episodes of UI (i.e. continence is achieved)
- UI response at several levels (i.e. ≥30% improvement, ≥50% improvement, ≥75% improvement etc.)
- no IDCs on urodynamic assessment (i.e. urodynamic cure is achieved) (urodynamic subset only).

Duration of effect following the first and subsequent treatments measured by:

**PAGE 39/139** 

- time to request retreatment
- time to eligibility for retreatment
- time between treatments.

# 3.2.2.2 Hierarchical Analysis of Secondary Endpoints

A hierarchical analysis will be performed in the order listed for the following secondary efficacy endpoints at Week 6 after the first IMP administration:

- (1) **Proportion of subjects with no episodes of UI** (i.e. continence is achieved):
  - measured by 7-day bladder diary.
- (2) Mean change from study Baseline (assessed at Screening) in the **I-QoL total summary score**:
  - measured by patient-reported questionnaire.

See Section 9.3 for further details regarding control of type one error for these secondary efficacy endpoints. See Table 19 in Section 7.2 for the full list of secondary efficacy endpoints for both the initial treatment and for retreatments.

# 3.2.3 Safety Endpoints and Evaluations

Safety will be assessed throughout the study by evaluating:

- AEs
- vital signs
- laboratory blood parameters (haematology and serum chemistry)
- laboratory urine parameters (laboratory urinalysis/microscopy, culture and sensitivity)
- development of BTX-A antibodies
- usage of concomitant medications and therapies.

Timepoints for safety evaluations are detailed in Table 4 and Table 5.

# 3.3 Randomisation and Blinding

#### 3.3.1 Randomisation

The randomisation will be done in a 2:2:1:1 ratio to one of four treatment sequences:

Sequence	Subjects	Treatment 1	Subsequent retreatment(s)
1	110 subjects	600 U Dysport®	600 U Dysport®
2	110 subjects	800 U Dysport®	800 U Dysport®
3	55 subjects	Placebo	600 U Dysport®
4	55 subjects	Placebo	800 U Dysport®

During analysis of study Treatment 1, the two placebo containing sequences will be pooled into a single arm.

Randomisation will be stratified by:

- 1) Aetiology of NDO (SCI or MS)
- 2) Previous intradetrusor BTX-A usage for UI (BTX-A naive vs. BTX-A non-naive in the bladder).

The sponsor's randomisation manager who is a statistician independent from the study, will prepare three lists which will be performed in blocks and will be based on computer-generated randomisation lists:

PAGE 40/139

- List A: a list of randomisation numbers, which will be produced in an unbalanced ratio 2:2:1:1 for the four treatment sequences and which will be stratified by aetiology and prior intradetrusor BTX-A usage for UI
- List B: a list of double blind treatment numbers, which will be specified on the treatment packs to be dispatched to the sites in order to dispense the drug in Treatment 1 and possibly for subsequent retreatments. It will be produced in a balanced ratio 1:1:1 for 600 U Dysport®, 800 U Dysport® and placebo
- List C: a list of double blind treatment numbers, which will be specified on the treatment packs to be dispatched to the sites in order to dispense the drug for retreatments (but not in Treatment 1). It will be produced in a balanced ratio 1:1 for 600 U Dysport® and 800 U Dysport®.

In order to maintain a balanced treatment sequence ratio of 2:2:1:1 in both the urodynamic and non-urodynamic subsets, the randomisation number(s) may be skipped in accordance with the procedure below. The purpose of skipping randomisation number(s) will be to ensure that the number of subjects in each treatment sequence will remain within five subjects of the required number to maintain a treatment sequence ratio of 2:2:1:1 within the subset. Any skipped randomisation number(s) will then be used in priority at subsequent randomisations. This process will be programmed into the interactive response technology (IRT) and will occur automatically (with no human intervention).

Using the following values for the concerned subset:

a = number of subjects in sequence 1

b = number of subjects in sequence 2

c = number of subjects in sequence 3

d = number of subjects in sequence 4

The IRT will skip randomisation number(s) to maintain the following conditions:

- RANGE(a/2,b/2,c,d)<5
- RANGE(a,b)<5
- RANGE(c,d)<5
- RANGE(a,c+d)<5
- RANGE(b,c+d)<5
- RANGE(a+c,b+d)<5

The assignment of randomisation and treatment numbers at drug dispensing (at Treatment 1 and subsequent retreatments) will be managed by IRT.

After eligibility is confirmed at the Treatment Visit (Day 1), subjects will be assigned by IRT to a randomisation number and to the associated treatment sequence, in a sequential order within each site (and within each level of strata). A treatment number will also be allocated by the IRT each time the drug is dispensed, according to the allocated treatment sequence. The IRT will also manage all the logistical aspects of treatments and associated incidents (e.g. drug supplies, replacement of lost, damaged, quarantined, expiring and expired kits).

PAGE 41/139

This service provides investigators, site co-ordinators and project team members with a 24 hour per day, 7 day per week service (additional details may be found in the IRT reference manual provided to each site). In case of medical or technical randomisation or dispensation queries, a 24-hour helpline is available see supporting information in the investigator site file.

Randomised subjects who terminate their study participation for any reason before administration of the first dose of randomised IMP will retain their randomisation and treatment numbers (i.e. these numbers will not be reused). The next subject will be given another randomisation number and another treatment number, even if he/she should receive the same treatment.

Subjects who leave the study early will not be replaced.

The sponsor's randomisation manager will keep the master lists. A copy of the list of treatment numbers (Lists B and C) will be confidentially supplied to the Chemistry Manufacturing and

to the Contract Research Organisation (CRO) in charge of IRT. Similarly, a copy of the list of randomisation numbers (List A) will also be confidentially supplied to the CRO in charge of IRT will be kept confidential in a secure location. Access to the randomisation lists must be restricted until authorisation is given to release them for final analysis.

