## 9.2 Sample Size Determination

The sample size is based on the ability to detect a statistically significant treatment difference in the weekly number of UI episodes at Week 6 following treatment in the two Dysport® arms compared to the placebo arm.

Assuming a decrease of 21 UI episodes per week in each Dysport® arm and a decrease of 12 UI episodes per week in the placebo arm, with a common standard deviation of 20 UI episodes, 80% power, and an alpha of 0.025 (as testing of both the 600 U and 800 U doses vs. the placebo

PAGE 103/139

dose will be performed simultaneously), a sample size of N=96 subjects per dose group for the primary analysis (a total of 288 subjects) is needed.

Assuming a treatment group random allocation ratio 1:1:1, a sample size of 106 subjects in each treatment group will have 80% power to detect a difference in UI of 9 episodes (the difference between UI in Dysport® 600 U and Dysport® 800 U groups and in placebo group assuming a common standard deviation equal to 20 episodes and a dropout rate equal to 10% with a 0.025 two-sided type one error rate. A total of 318 subjects would therefore need to be enrolled.

However, in order to ensure that the development program will deliver adequate Dysport exposure data to meet ICH E1 guideline recommendations, a total of 330 subjects are planned to be randomised.

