2.3 Sample Size and Power

The sample size is based on the ability to detect a statistically significant treatment difference in the weekly number of UI episodes at Week 6 following the first IMP administration in the two Dysport arms (600 U and 800 U) compared to the placebo arm.

Assuming a weekly decrease of 21 UI episodes in each Dysport arm and a weekly decrease of 12 UI episodes in the placebo arm, with a common standard deviation of 20 UI episodes, 80% power, and an alpha of 0.025 (as testing of both the 600 U and 800 U doses vs. the placebo dose will be performed simultaneously), a sample size of 96 subjects per dose group (a total of 288 subjects) is needed. Dropout between randomisation and Week 6 (primary efficacy timepoint) is expected to be 10%, and thus a total of 318 subjects would be needed to be enrolled. However, in order to ensure that the development program will deliver adequate Dysport exposure data to meet ICH E1 guideline recommendations, a total of 330 subjects are planned to be randomised. Subjects who leave the study early will not be replaced.

Sample size calculations were performed in SAS Studio 3.6.

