7.6.3 Primary Efficacy Analysis

The primary efficacy endpoint is mean change in the weekly number of UI episodes from study baseline to Week 6 after the first treatment. Seven-day bladder diaries that contain data recorded on at least 5 days will be included in the analysis.

As all subjects should have visits up to and including week 12, but thereafter visits are dependent on whether the subject receives retreatment, statistical testing between treatment

Statistical Analysis Plan

Version: Final v1.0

September-2018

Ipsen Protocol No. D-FR-52120-223

000000146513

Date of Issue: 21-

Covance Study ID:

groups will be performed only up to Week 12, inclusive. Descriptive statistics table will present any timepoint.

Weekly number of UI episodes and the mean change from study baseline will be presented for the DBPC Cycle. The mixed model repeated measures (MMRM) analysis will be conducted with the change of the weekly number of UI episodes from study baseline as response variable. Fixed effect variables include treatment group, visit (Week 2, Week 6 and Week 12), treatment-by-visit interaction, stratification variables [the aetiology of NDO and prior intradetrusor BTX-A usage for UI] and study baseline value of weekly number of UI episodes. Random effect will include the subject effect. An unstructured covariance matrix will be specified in the mixed model to account for within subject correlation. If model fails to converge, the structure of first order autoregressive AR (1), compound symmetry (CS) or variance components (VC) will be used.

The least square means (LSMEANS) of the change of weekly number of UI at each visit in each group with standard error, the difference of mean between the two treatment groups at each visit, the 95% CI of the difference and the p-value for treatment group will be presented. The comparison of main interest will be treatment difference at Week 6.

The SAS codes of MMRM for reference are below.

CCI
[Redacted SAS code]

The validity of the model assumptions of normality will be investigated using residual plots. The LS means of change from study baseline for weekly UI in the DBPC and Dysport Cycles will be presented in line plots by treatment groups.

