7.6.5 Hierarchical Analysis of Secondary Efficacy Endpoints

As specified in Section 7.6.12, a hierarchical analysis will be performed in the order listed for the following two secondary efficacy endpoints at Week 6 after the first IMP administration:

- 1) Proportion of subjects with no episodes of UI (i.e. continence is achieved)
- 2) Mean change from study Baseline in the I-QoL total summary score

The Derivation rules are specified in Section 3.2 and Appendix II.

For 1), a logistic generalised linear mixed model (GLMM) for repeated measures will be fitted for UI responses using repeated measurements at Week 2, Week 6, and Week 12. The “proportion of subjects with no episodes of UI” will be analysed as a response variable, the model will include treatment group, stratification variables, study baseline value, visit (week 2, week 6 and week 12), study baseline*visit and treatment*visit interactions as fixed effect. The study baseline value will be weekly number of UI episodes. The logistic GLMM is fitted using the logit link and the binomial distribution. Odds ratios, 95% CIs of odds ratio, and p-values for treatment group comparisons at each visit (week 2, week 6 and week 12) will be presented.

The SAS codes of GLMM for reference are below.

CCI [redacted]
 [redacted]
 [redacted]
 [redacted]
 [redacted]
 [redacted]
 [redacted]
 [redacted]
 [redacted]

In above codes, the variables are defined as:

CCI [redacted]
 [redacted]

CCI

For 2), MMRM model will be fitted using the “mean change” endpoint, as the response variable to obtain the p-value of treatment groups. The model will be the same as primary analysis model in section 7.6.3. The least square means of change at Week 6 in each group with standard error, the mean difference of pairwise comparison, the 95% CI of the difference and the p-value for the treatment groups will be presented for each model.

If the testing procedure is stopped at the end of any particular step, the outcomes of the following steps will be presented and used for description only and no formal statistical conclusion will be drawn.

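### The primary MMRM omits the urodynamic subset that allocation is balanced on, and the baseline-by-visit term used in the continence model; its standard error may therefore be somewhat too large

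*Protocol*

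**What the plan says.** **Allocation.** Protocol 3.3.1 stratifies the randomisation list by aetiology (SCI or MS) and by prior intradetrusor BTX-A use. It then adds a further constraint: "In order to maintain a balanced treatment sequence ratio of 2:2:1:1 in both the urodynamic and non-urodynamic subsets", the IRT may skip randomisation numbers automatically and use them later. Among its limits, within a subset the count in each Dysport arm must stay within fewer than five of the pooled placebo count. Protocol 3.1 plans at least 200 subjects in the urodynamic subset and explains that the non-urodynamic subset exists because some sites cannot perform standardised urodynamics.

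**Primary model.** SAP 7.6.3 specifies an MMRM with treatment, visit, treatment-by-visit, "stratification variables [the aetiology of NDO and prior intradetrusor BTX-A usage for UI] and study baseline value of weekly number of UI episodes", and an unstructured covariance matrix. The protocol synopsis and Protocol 9.4.5 name no further covariate. Protocol 9.4.6 plans no adjustment for country or site.

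**Other models.** The continence GLMM in SAP 7.6.5 includes "study baseline*visit and treatment*visit interactions as fixed effect", and SAP 7.6.6.1.1 reuses that model for the responder thresholds. The I-QoL model in 7.6.5 is the same as the primary model. The Week 6 ANCOVA in SAP 7.6.4.2 has the two strata and baseline but no subset.

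**The concern.** An analysis should normally account for the factors that constrain allocation. Balancing on a prognostic factor removes its variance from the treatment comparison. A model that leaves the factor out keeps that variance in the residual and so reports a standard error larger than the true one. Subset could be prognostic here. It follows from what a site can do, so it may carry site differences that nothing else in the model captures.

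The baseline term raises a separate question. With one slope for three visits, any gap between the Week 6 slope and the common slope stays in the Week 6 residual. The SAP allows the slope to vary by visit in its continence model but not in its primary model.

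At stake is efficiency on the primary endpoint. It would count most if one dose failed and the other had to reach the 0.025 level under the Hochberg rule.

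**Working it through.** **1. The plan's own figure.** Inputs from SAP 2.3: "Assuming a weekly decrease of 21 UI episodes in each Dysport arm and a weekly decrease of 12 UI episodes in the placebo arm", a difference of 21 − 12 = 9; "with a common standard deviation of 20 UI episodes"; "80% power, and an alpha of 0.025". Protocol 9.2 adds the sidedness, "with a 0.025 two-sided type one error rate", and the 1:1:1 ratio.

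Normal approximation: n = 2 × (2.2414 + 0.8416)² × (20/9)² = 2 × 9.505 × 4.938 = 93.9, so 94 per group. The noncentral t gives 79.9% power at 95 and 80.4% at 96, so the stated 96 reproduces. At 96 per arm the unadjusted SE is 20 × √(2/96) = 2.887, with power 81.0% (normal approximation). At 110 × 0.9 = 99 evaluable per arm, power is 82.2% (normal) or 81.7% (t). These figures use an unadjusted SD of 20, so they depend on neither missing term.

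**2. Subset, closed form.** With p = 200/330 = 0.606, p(1 − p) = 0.2388. Let D be the difference between subsets in UI change, given the other covariates. The documents give no D, so the values are assumptions. Variance share R² = 0.2388 × D²/400, and the SE is multiplied by √(1 − R²).

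| D (episodes/week) | R² | SE at 96 per arm | Change | Power |
|---|---|---|---|---|
| 0 | 0 | 2.887 | 0 | 81.0% |
| 2 | 0.0024 | 2.883 | −0.1% | 81.1% |
| 4 | 0.0096 | 2.873 | −0.5% | 81.4% |
| 6 | 0.0215 | 2.856 | −1.1% | 81.9% |
| 9 (as large as the treatment effect) | 0.0483 | 2.816 | −2.4% | 83.0% |

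**3. Baseline-by-visit, closed form.** Let d be the gap between the Week 6 slope and the common slope. R² = d² × (baseline SD)²/400. Neither d nor the baseline SD is in the documents; the range assumed for the SD is 10 to 25.

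| d | Baseline SD | R² | Change in SE | Power |
|---|---|---|---|---|
| 0 | any | 0 | 0 | 81.0% |
| 0.1 | 10 to 25 | 0.0025 to 0.0156 | −0.1% to −0.8% | 81.1% to 81.6% |
| 0.2 | 10 to 25 | 0.0100 to 0.0625 | −0.5% to −3.2% | 81.4% to 83.6% |

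A gap of 0.2 is demanding. The common slope includes Week 6, so with equal weights the Week 2 and Week 12 slopes must average 0.3 away from it (2/3 × 0.3 = 0.2).

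**4. Simulation of the MMRM.** Settings: 96 per arm, complete data, subset share equal across arms, total Week 6 variance 400, baseline SD 20, Week 6 slope −0.5, 600 runs per scenario. All but the 96 and the 400 are assumptions. Entries are the mean reported SE at Week 6.

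| Scenario | SAP terms | + subset | + baseline-by-visit | Both |
|---|---|---|---|---|
| D = 0, equal slopes | 2.511 | 2.507 | 2.511 | 2.507 |
| D = 4, equal slopes | 2.506 | 2.487 | 2.506 | 2.487 |
| D = 9, equal slopes | 2.513 | 2.427 | 2.513 | 2.427 |
| D = 0, slopes −0.3/−0.5/−0.4 | 2.533 | 2.529 | 2.511 | 2.508 |
| D = 9, slopes −0.3/−0.5/−0.4 | 2.538 | 2.453 | 2.516 | 2.430 |

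The falls are 0.8% (D = 4, subset), 3.4% (D = 9, subset), 0.9% (unequal slopes, baseline-by-visit) and 4.3% (D = 9 with unequal slopes, both). The 0.004 fall in the first row comes from a fixed residual divisor and is not a gain; the other subset figures include about the same amount. The falls exceed step 2 because baseline already explains (0.5 × 20)² = 100 of the 400. At D = 9 subset then accounts for 19.3/300 = 6.4%, and √(1 − 0.064) = 0.967.

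**5. What the subset term changes.** At D = 9 with equal slopes, adding subset moved the reported SE from 2.513 to 2.427. The spread of the estimates themselves went only from 2.423 to 2.416 (2.630 to 2.629 at D = 4). Balance had already taken subset variance out of the estimate, and the model without subset did not credit it. With 600 runs each spread carries a Monte Carlo error of about 1/√1200 = 2.9%, so only these before-and-after comparisons on the same data are informative. For baseline-by-visit, the spread fell from 2.472 to 2.448 in one unequal-slope scenario and went from 2.439 to 2.444 in another. The simulation is too small to settle so small a real gain.

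**The case against.** **The SAP follows its protocol.** The protocol names two stratification variables, repeats them as covariates, and declines site adjustment. The IRT skips a number only when a tolerance would be breached. This is true, and it means that adding terms changes the protocol's covariate list. It does not justify the omission. With 200 in the subset, about 67 per arm, holding the arm counts to a difference below five is a real constraint whatever it is called. Declining to adjust for some 90 sites is also a different decision from leaving out one binary balancing factor.

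**The benefit is assumed.** This stands. A reader might infer that the primary standard error is in fact larger than needed. The documents do not say that UI change differs by subset or that the slope changes over visits.

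**Precision is not lost on subset.** This stands too. A reader might infer that omitting subset makes the estimate noisier, biased or prone to false positives. Step 5 shows the estimate hardly changes; any error is in the reported SE, on the conservative side.

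**Some of this is already covered, or does not carry over.** The Week 6 ANCOVA already fits a Week 6 slope, though only as a sensitivity analysis. I-QoL is collected after baseline only at Weeks 6 and 12 in this window, so the three-visit slope argument does not fit it. In a logistic model, adding a prognostic covariate usually raises the SE of the log odds ratio and changes the conditional odds ratio being estimated. The variance argument therefore gives no ground for adding subset to the continence GLMM.

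**Only the text can be checked.** The model code is redacted, so this point rests on the written list of terms.

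**Conclusion.** Both omissions are present in the text, and no reason is given for either. If subset predicts UI change given baseline and strata, the reported SE is too large and the primary test conservative. If the baseline slope differs by visit, the common slope loses some precision at Week 6. Under the assumed values above, the SE falls by about 0 to 4% across both terms, and power rises by about 0 to 3 points for either term alone. The gain is zero if neither condition holds.

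This is a minor, inexpensive improvement. A reader might infer that the trial is underpowered or its primary result unsafe. Neither follows: planned power exceeds 80% without these terms, and the treatment comparison stays valid without them.

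**What to change.** Amend the SAP before database lock:

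- In the 7.6.3 MMRM, add urodynamic subset (yes/no, as recorded in the IRT at randomisation) and baseline-by-visit as fixed effects.
- Add subset to the Week 6 ANCOVA in 7.6.4.2 and to the I-QoL MMRM in 7.6.5. SAP 7.6.6.2 borrows the ANCOVA for the urodynamic endpoints, where every subject is in the subset, so state that the term drops out there.
- Leave the continence GLMM as it is unless a separate reason is given for adding subset.
- Record the departure from the protocol's covariate list in SAP Section 8, now marked not applicable.

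If the sponsor prefers to keep the current model, a sentence explaining why the two terms are left out would do.

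The cost is SAP wording, the Section 8 entry, and three parameters in the primary model (one for subset, two for baseline-by-visit) against roughly 290 evaluable subjects. No new data are needed: the SAP already defines the urodynamic population by subset at randomisation.
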